2.1 Primary Objective

The primary objective of this study is to evaluate the efficacy of 0.005%, 0.002%, and 0.0008% estriol vaginal gel and to determine the minimal effective dose for the treatment of postmenopausal vaginal atrophy in women that refer moderate to severe vaginal dryness as the most bothersome symptom.

2.2 Secondary Objectives

The secondary objectives of this study are to:

- Evaluate the efficacy of the three formulations of estriol vaginal gel in the improvement of other symptoms and signs of vulvovaginal atrophy.
- Evaluate the safety and tolerability of the three formulations of estriol vaginal gel.

2.3 Exploratory Objectives

The exploratory objectives of this study are to:

- Evaluate the final subjective global perception of efficacy of the three formulations of estriol vaginal gel.
- Evaluate the subject's acceptability of the three formulations of estriol vaginal gel.

3 Investigational Plan

3.1 Study Design

This study is a double-blind, randomized, dose-ranging, placebo-controlled multicenter study with four parallel groups. Approximately 25 sites in Europe will be included in the study. The study setting will include academic hospitals and gynecological clinics. The study population is postmenopausal women who report moderate to severe vaginal dryness as their most bothersome symptom in addition to other symptoms and/or signs of postmenopausal vulvovaginal atrophy.

After providing informed consent, potential subjects will be evaluated during the screening period to determine if they are eligible to participate in the study. A screening identification number will be assigned to each eligible subject according to their order of arrival into the study at screening visit. Subjects who meet all of the inclusion criteria (see Section 4.1.1) and none of the exclusion criteria (see Section 4.1.2) will be randomized into the study. A total of 280 subjects will be enrolled and randomly allocated to one of the four treatment groups (0.005%, 0.002%, or 0.0008% estriol vaginal gel or placebo vaginal gel); the allocation to treatment group will be 1:1:1:1. A blocked randomization across the entire study (i.e. all sites as a whole) will be used. Subjects will be assigned a randomization code according to their order of arrival into the study at the Baseline Visit. Initial treatment consists of daily vaginal administration of 1 gram of randomly-assigned estriol gel or placebo gel using the supplied applicator. After 21 days of daily administration, treatment will continue with twice-weekly administration up to Week 12 (i.e., Mondays and Thursdays).

The duration of trial participation for each woman is expected to be approximately 20 weeks (from Screening to End-of-Study phone call) although the time on study drug will be approximately 12 weeks. Subject completion is defined as the completion of all phases of the study, including the End-of-Study phone call to be performed for safety purposes at Week 16.

An overview of the study visit procedures is given in the Schedule of Events (Table 1). Details of specific procedures and testing are provided in Section 6.

Table 1: Schedule of Events

Procedure	Screening Visit	Baseline	Week 3	Week 8	Week 12/ Early Termination	Week 16/ End of Study Phone Call
Visit Window (days)	-30 to -1	1	21 ±3	56 ± 5	84 ± 5	112 ± 5
Informed consent	X					
Randomization		X				
Medical history, medication history, and demographics	X					
Physical examination ^a	X				X	
12 lead electrocardiogram ^b	X				X	
Gynecological examination ^c	X				X	
Transvaginal ultrasound (women who have a uterus)	X				X	
Mammogram (if no negative mammogram documented within 9 months prior to randomization) ^d	X					
Clinical laboratory tests ^e	X				X	
Endometrial biopsy (women who have a uterus)	X				X	
Adverse event reporting ^f	X	X	X	X	X	X
Concomitant medication reporting	X	X	X	X	X	X
Evaluation of vaginal dryness ^g	X		X		X	
Evaluation of symptoms and signs of vulvovaginal atrophy ^{g, h}		X	X		X	
Vaginal pH	X		X		X	
Vaginal smear for evaluation of vaginal cytology	X		X		X	
Evaluation of global efficacy ⁱ					X	
Evaluation of acceptability ^j					X	
Administration of the first dose of the study medication ^k		X				
Study drug and supply dispensing ^l		X	X	X		
Reconciliation of returned study drug			X	X	X	

Table 1: Schedule of Events

Procedure	Screening Visit	Baseline	Week 3	Week 8	Week 12/ Early Termination	Week 16/ End of Study Phone Call
a	Physical examination to include vital sign measurements (height [Screening visit only], weight, blood pressure, heart rate).					
b	Two ECG exams will be performed in each of these two visits, about 5 minutes apart one from another.					
c	Gynecological examination to include visual inspection of external genitalia, speculum examination of vagina and cervix (if present), bimanual palpation of uterus and ovaries (if present), breast palpation. Papanicolaou exam will be performed only at screening visit.					
d	Neither mammograms performed as study specific procedure nor negative mammogram documented within 9 months prior to randomization will be recorded in the eCRF but archived in subject's clinical records					
e	Laboratory testing performed under fasting conditions at Screening and Week 12 includes: standard hematology panel plus prothrombin time, activated thromboplastin partial time, fibrinogen, antithrombin III/protein C/protein S; standard chemistry panel (glucose, cholesterol, high-density lipoprotein, low-density lipoprotein, triglycerides albumin, alanine aminotransferase, aspartate aminotransferase, creatine phosphokinase, bilirubin, creatinine, total protein, uric acid, blood urea nitrogen); hormones (estradiol, estriol, estrone, follicle-stimulating hormone, luteinizing hormone); and standard urinalysis with microbiology. Factor V Leiden testing will be performed only at screening visit (or Week 12/ET visit if not obtained at screening)					
f	AEs and SAEs will be recorded from screening (post ICF signature) and subsequently at every study visit and up to 30 days post last study drug administration. Tolerability of study drug will be evaluated at weeks 3, 8, 12, and 16.					
g	For the evaluation of symptoms and signs, each symptom and each sign will be graded as: 0=absent; 1=mild; 2=moderate; 3=severe					
h	Signs and symptoms other than vaginal dryness to be evaluated are the following: Symptoms: dyspareunia, pruritus or itching, burning, dysuria. Signs: pallor, friability, thinning or flattening of folds, presence of petechiae, and dry mucosa					
i	Global efficacy will be assessed as: highly efficacious, efficacious, non-efficacious, detrimental					
j	Global acceptability will be assessed as: excellent, good, acceptable, unacceptable					
k	The investigator will administer the first study medication or will supervise the patient doing the administration					
l	Medication kits will be dispensed via IWRS					

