12.4	Screening Criteria - Excluded Medications	84

List of Tables

Table 1: Schedule of Events.....	20
Table 2 Assumed Proportions for Wilcoxon Rank Sum Test of Vaginal Dryness	57
Table 3: Gatekeeping Procedure for Efficacy Analyses.....	60

List of Figures

Figure 1: Estriol Structural Formula	30
--	----

Protocol Synopsis

Protocol Number:	ITFE-2092-C1
Title:	A Phase 2, Dose-ranging, 12-week, Randomized, Double-blind, Placebo-controlled, Parallel-group Study Evaluating the Efficacy and Safety of Three Formulations of Ultra-low Dose Estriol Vaginal Gel (0.005% Estriol Vaginal Gel, 0.002% Estriol Vaginal Gel, 0.0008% Estriol Vaginal Gel) for the Treatment of Vaginal Dryness in Postmenopausal Women with Vulvovaginal Atrophy
Sponsor:	ITF Research Pharma SLU [name] [name]
Study Phase:	Phase 2
Study Sites:	Approximately 25, in 5 European countries (Spain, Italy, Sweden, Hungary, Czech Republic).
Indication:	Treatment of vaginal dryness in postmenopausal women with vulvovaginal atrophy
Rationale:	Local estrogen therapy is the recommended approach to treat symptoms related to postmenopausal vulvovaginal atrophy. An estriol-based formulation allowing a lower dose per application provides reduced estrogen exposure while maintaining efficacy, resulting in fewer systemic effects and a more favorable risk-benefit ratio for the patient.
Objectives:	
Primary objective: Evaluate the efficacy of 0.005%, 0.002%, and 0.0008% estriol vaginal gel and determine the minimal effective dose for the treatment of postmenopausal vaginal atrophy in women who report moderate to severe vaginal dryness as the most bothersome symptom.
 
Secondary objectives: Evaluate the efficacy of the three formulations of estriol vaginal gel in the improvement of other symptoms and signs of vulvovaginal atrophy.
 
Evaluate the safety and tolerability of the three formulations of estriol vaginal gel.
 
Exploratory objectives: Evaluate the final subjective global perception of efficacy of the three formulations of estriol vaginal gel.
 
Evaluate the subject's acceptability of the three formulations.

Subject Population:

Inclusion criteria:

1. Capable of understanding the written informed consent, provides signed and witnessed written informed consent, and agrees to comply with the protocol procedures and assessments
2. Age ≥ 40 and ≤ 80 years

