6.1.2 Baseline Visit

This visit will be performed on Day 1. The following procedures will be performed:

- Randomization: the investigator should randomize the subject through IWRS in which a randomization code and study drug kits will be allocated
- Gynecological examination including evaluation of symptoms and signs of vulvovaginal atrophy other than vaginal dryness
- Recording of adverse events since Screening Visit
- Recording of concomitant medications
- Administration of first dose of study drug by the investigator or by the subject in presence of the investigator Dispensing of dosing instructions and adequate medication supplies for 3 weeks (three medication kits)

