7.8.1 Analysis of Primary Efficacy Endpoints

The changes from baseline to Week 12 in vaginal dryness will be analyzed using a Wilcoxon Rank Sum test, controlled for country, to obtain the p-values. The Hodges-Lehmann estimate of median difference between treatment groups (0.005% versus placebo, 0.002% versus placebo and 0.0008% versus placebo) will also be presented with 95% confidence intervals. It should be noted that, since the statistical tests are one-sided, only one limit of each confidence interval is of particular interest for analysis. Details of statistics to be presented will be described in the Statistical Analysis Plan. Missing values at Week 12 will be estimated using the last observation carried forward (LOCF). Only post-Baseline values will be carried forward.

The changes from baseline to Week 12 in vaginal pH, and the changes in proportions of parabasal and superficial cells will be analyzed using a parametric ANCOVA model. The model will include fixed effects of treatment and country, and the baseline value will be used as a covariate. The adjusted (least-square) mean change from baseline to Week 12 will be presented for each treatment, along with the corresponding standard error. The difference in adjusted means between treatment groups (0.005% versus placebo, 0.002% versus placebo and 0.0008% versus placebo) will also be presented with 95% confidence intervals and p-values. It should be noted that, since the statistical tests are one-sided, only one limit of each confidence interval is of particular interest for analysis. Model assumptions will be examined and, if required, a Wilcoxon Rank Sum test as described for vaginal dryness will be used. Missing values will be estimated using LOCF. Only post-Baseline values will be carried forward.

No adjustment for multiplicity will be made, since statistical significance in all four co-primary endpoints is required to declare efficacy.

The robustness of the LOCF approach for missing data will be addressed by completing a sensitivity analysis. This will be an observed case analysis and will use no imputation methods in order to assess the robustness of the results.

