6.1.3 Pooling of Investigative Sites

Sites will be pooled according to country for inclusion as an effect in the statistical models. It is recognized that the pooling of sites in this manner preserves the inclusion of all randomized subjects in the analysis. However, the result of pooling is a loss of the “individuality” of each site being pooled as well as the potential for the pooled site to be associated with an inflated sample size compared to sites that do not require pooling. The effect of this cannot be determined a priori but it is an acceptable approach for the retention of subjects in the analysis.

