6.3.1.1 Change from Baseline to Week 12 in Severity of Vaginal Dryness

Vaginal dryness is one of the five symptoms of vulvovaginal atrophy, and is self-assessed by the subject at the Screening, Week 3 and Week 12 / Early Termination visits.

Each symptom will be scored by the subject using a numeric scale from 0 to 3, as follows:

0	Absent:	The symptom is not present
1	Mild:	The symptom is of mild intensity
2	Moderate:	The symptom is of moderate intensity
3	Severe:	The symptom is severe in intensity

The number and percentage of subjects with each severity of vaginal dryness at each visit will be summarized by treatment in a general summary table of symptoms of vulvovaginal atrophy.

Given that the Inclusion Criteria for the study require the subject to have moderate (score of 2) or severe (score of 3) vaginal dryness at Baseline (Screening), the change from Baseline to Week 12 may take the possible values ranging from -3 (Severe at Screening; Absent at Week 12) to 1 (Moderate at Screening; Severe at Week 12).

The number and percentage of subjects with each ordinal change from Baseline to Week 12 value (-3, -2, -1, 0 and 1) will be summarized by treatment group.

The change from Baseline to Week 12 in vaginal dryness will be analyzed using a Wilcoxon Rank Sum test, controlled for country, to obtain the one-sided p-values for each treatment

comparison (0.005% Estriol versus placebo, 0.002% Estriol versus placebo and 0.0008% Estriol versus placebo) by means of the FREQ procedure in SAS with the SCORES = RANK option. The Hodges-Lehmann estimate of median difference between treatment groups will also be presented for each of the three treatment comparisons above, along with 95% CIs, by means of the NPAR1WAY procedure in SAS. Hodges-Lehmann estimates will be presented without the adjustment for country, since SAS does not currently produce Hodges-Lehmann estimates when covariates are included. Missing values at Week 12 will be estimated using LOCF methodology for the ITT population analysis only. Only post-Baseline values will be carried forward.

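### One randomization list serves all sites although every co-primary analysis controls for country, which costs a little precision that country strata would keep

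*Protocol*

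**What the plan says.** Protocol 3.1 and SAP 3 both describe a single list: "A blocked randomization across the entire study (i.e. all sites as a whole) will be used", with "the allocation to treatment group will be 1:1:1:1" and codes issued in order of arrival. Part of Protocol 5.1 is redacted, but 3.1 is explicit and no visible text names a stratification factor. Allocation is already central. Under Protocol 6.1.2, "the investigator should randomize the subject through IWRS in which a randomization code and study drug kits will be allocated". The synopsis lists about 25 sites in five countries.

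The analyses do use country. SAP 6.1.3 says: "Sites will be pooled according to country for inclusion as an effect in the statistical models". Protocol 7.8.1 analyses dryness by a "Wilcoxon Rank Sum test, controlled for country, to obtain the p-values". For pH and for superficial and parabasal cells it specifies an ANCOVA: "The model will include fixed effects of treatment and country, and the baseline value will be used as a covariate". For the dryness effect size, SAP 6.3.1.1 says "Hodges-Lehmann estimates will be presented without the adjustment for country", and gives a SAS limitation as the reason.

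**The concern.** The plan treats country as important enough to control for in all four co-primary tests, but not at allocation, and does not say why. A test controlled for country draws only on contrasts between arms inside the same country. A country where the two arms differ in size contributes less than its number of women would suggest, and a country with no woman in one of the two arms contributes nothing to that dryness comparison.

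Dryness sets the sample size. A dose must succeed on all four co-primary endpoints before the next lower dose can be tested, so any power lost on dryness is carried down the sequence. The dryness effect estimate has no country adjustment, so its agreement with its own p-value depends partly on how evenly the arms happen to fall across countries.

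**Working it through.** **Inputs from the documents:** 280 women, four equal arms of about 70, five countries, one-sided 0.025, 90% power at 57 per group for dryness, 18% drop-out (Protocol 7.5; SAP 6.1.4). **Assumed, because the documents do not give them:** country shares (from equal to 50/20/15/10/5%), block size 8, and any difference in response between countries.

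**1. The plan's own figure.** From the assumed dryness proportions, P(estriol better) = 0.189×0.882 + 0.423×0.686 + 0.270×0.333 = 0.5468 and P(tie) = 0.2398. The win probability is 0.5468 + 0.2398/2 = 0.6667. At 57 per group the calculated power is 90.7% and the simulated power 90.3%. 57/0.82 = 69.5, rounded up to 70 per arm, or 280. The stated size reproduces. It makes no allowance for country.

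**2. Pairwise comparison within countries (dryness).** Measure information by the sum over countries of nE×nP/(nE+nP). For a country with m women in the two arms and nE = m/2 + x, the term is m/4 − x²/m. With one list, the expected x² is (m/4)×(M−m)/(M−1), where M is the two-arm total. Summed over five countries, the expected loss is M/(M−1) out of M/4, a fraction 4/(M−1) whatever the country shares. At M = 140 this is 4/139 = 2.9%, which agrees with the simulated 97.1% retained (99.7-100% with strata).

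With 18% loss and blocks of 8, simulated information is 27.6-27.7 for the single list and 28.4-28.5 with strata:
- 27.7/28.4 = 0.975 and 27.6/28.5 = 0.968, a loss of about 2.5-3%.
- As information is n/2 for balanced arms of n, this is 2×0.7 = 1.4 to 2×0.9 = 1.8 evaluable women per arm.

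**3. Power.** Power = Φ(3.2416×√r − 1.96), where r is the information ratio and 3.2416 = 1.9600 + 1.2816. For r = 0.975 it is 89.3%, and for r = 0.97 it is 89.1%, so 0.7-0.9 points are lost. Direct simulation of a stratified Wilcoxon test with van Elteren weights and no country effect gives 89.1% against 90.1% at 57 per arm, and 94.4% against 94.8% at 70. With 8,000 replicates each, the standard error of such a difference is about √(2×0.9×0.1/8000) = 0.5 points, so the two results agree.

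**4. Four-arm ANCOVA (pH, superficial cells, parabasal cells).** All four arms help to estimate the country effects, so the corresponding approximation is 4/(280−1) = 1.4%. Simulation gives about 1.1-1.5%. For pH at 57 per arm, power moves by about 0.3 points.

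**5. Empty arm in a small country.** A 5% share is 14 women, or 3.5 per arm, and 2.87 per arm after 18% loss.
- No loss: e^(−3.5) = 0.030 per arm, so 1 − 0.970² ≈ 6% for one dose-placebo pair.
- 18% loss: e^(−2.87) = 0.057 per arm, so 1 − 0.943² ≈ 11% for one pair, and 1 − 0.943⁴ ≈ 21% for any of the four arms.

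Simulation agrees: about 5-6% and 10-12% for one pair. With strata the figure for one pair is about 0-2%. With equal shares the chance is essentially zero under either scheme.

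**6. The unadjusted dryness estimate.** The unadjusted win probability was used as a stand-in for the Hodges-Lehmann estimate.
- No country differences: strata change nothing (SD 0.0487 against 0.0484 at 57 per arm).
- Assumed country shifts of ±0.4 to 0.8 log-odds: the SD falls from 0.0493 to 0.0468 at 57 per arm and from 0.0453 to 0.0423 at 70, or 5-7%.
- The mean is the same under both schemes apart from simulation error (0.6525 and 0.6510; 0.6506 and 0.6511).

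**The case against.** Adjusting in the analysis for a factor that was not stratified at randomization is a valid design. Nothing here biases a comparison or inflates type I error. That stands, and it sets the weight of the point. Four further objections bear on its size.

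- **Which test.** The information sum in step 2 is not necessarily the weighting of the specified procedure. SAP 6.3.1.1 calls for PROC FREQ with rank scores. If that sums raw within-country ranks, the loss from the single list would be about 1.1-3.8%, depending on country shares. Power would be near 85% at 57 per arm under either scheme with moderately unequal countries, a larger matter that stratifying does not cure. So the dryness figure is indicative only.
- **Drop-out.** Removing 18% of women overstates the loss of data. The primary analysis carries post-baseline values forward, and efficacy is measured at Week 3 and at early termination, so many who stop early still count. The true position lies between 57 and 70 per arm, and at 70 dryness power is about 94%.
- **The empty-arm figure.** A reader might take the 21% for any of four arms as the risk to a result. For one comparison it is 5-12%, it requires an assumed 5% country, and it concerns only that country's small contribution.
- **The Hodges-Lehmann estimate.** A reader might infer that balance at allocation is its only protection, or that it is biased. The documents do not support either reading. Randomization keeps it free of systematic country bias, the SAP discloses and explains the missing adjustment, and the gatekeeping decision rests on a p-value that is controlled for country.

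**Conclusion.** The point holds as a small efficiency improvement. The single list loses about 2.5-3% of information in a pairwise country-stratified dryness comparison (under 1 point of power at the nominal 90%) and about 1-1.5% for the three ANCOVA endpoints. Country strata recover nearly all of it. The extra variability of the dryness estimate matters only if change in dryness differs by country, for which the documents give no figure.

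These sizes rest on assumed country shares and block size, and for dryness on how the rank-score test weights countries. It would be wrong to read the 2.5-3% as applying to every endpoint, or to conclude that the trial is invalid or materially underpowered as designed.

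**What to change.** If enrolment has not begun, change Protocol 3.1 and SAP 3 to blocked randomization stratified by country through IWRS, 1:1:1:1 within each country, and make Protocol 5.1 consistent. No analysis changes.

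The cost is a new IWRS list specification and two short text edits. The downside is up to five incomplete blocks at the end of recruitment, so final arm sizes may differ by a few women. The documents do not say whether enrolment has started. The change is useful only before it does, and a loss of this size would not justify altering the list afterwards.

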3.1.1 Rationale of Study Design

The study design is concordant with a dose response approach (three doses of estrogens will be tested and compared to placebo), as well as the indication and the estrogenic nature of the product, and thus follows the recommendations of the FDA in Draft Jan 2003 Recommendations for Clinical Evaluation of Estrogen/Progestins to Treat Vulvovaginal Symptoms.

A placebo arm has been included in the study as per the above referenced FDA recommendations, in which it is indicated to demonstrate a statistically significant improvement versus placebo in the primary efficacy analyses. By selecting placebo as comparator, all potential influences on the actual or apparent course of the disease other than those arising from the pharmacologic action of the test drug are controlled. Placebo-controlled trials measure the total pharmacologically mediated effect of treatment, and provide the maximum ability to distinguish adverse effects caused by a drug from those resulting from underlying disease or intercurrent illness. (ICH Guideline E10)

4 Subject Selection and Withdrawal Criteria

